4.5.2. Extent of Exposure

Duration of exposure to study medication will be calculated as follows:

$(\text{Stop date} - \text{start date}) + 1$.

The mean duration of exposure in days will be summarized by treatment group. Total exposure (in mL) will be based on the number of vials dispensed against the number returned (number of vials * contents of each vial (in mL)).

For in-clinic dosing, the RPL554 exposure will be calculated based on the nominal dose.

5. Efficacy Endpoints

5.1. Primary Efficacy Endpoint

- Change from baseline FEV₁ to peak FEV₁ (over 3 hours) at Week 4
 - Baseline is defined as the FEV₁ pre-dose assessment (-15 minutes) collected at Visit 2
 - Peak FEV₁ at Week 4 is defined as the maximum post-dose value among the 30 minutes, 1, 2 and 3 hour assessments collected at Visit 6 (Week 4).

5.2. Secondary Efficacy Endpoints

- Change from baseline FEV₁ to morning trough FEV₁ at Week 1, 2, 3 and 4
- Change from baseline FEV₁ to average FEV₁ (over 12 hours) at Day 1 and at Week 4
- Change from baseline FEV₁ to average FEV₁ (over 3 hours) at Day 1, Week 1, 2, 3, and 4
- Change from baseline FEV₁ to peak FEV₁ (over 3 hours) at Day 1, Week 1, 2 and 3

For details on the derivation of the above FEV₁ endpoints refer to section 5.5.1

- Change from baseline in EXACT-PRO E-RS score at Week 4
- Change from baseline in EXACT-PRO Total score at Week 4
- Change from baseline in EXACT-PRO E-RS Breathlessness score at Week 4
- Change from baseline in EXACT-PRO E-RS Cough/Sputum score at Week 4
- Change from baseline in EXACT-PRO E-RS Chest Symptoms score at Week 4

For details on the derivation of the above EXACT-PRO scores refer to section 5.5.2

- Change from baseline in the SGRQ-C Total score at Week 4
- Change from baseline in the SGRQ-C Symptoms score at Week 4
- Change from baseline in the SGRQ-C Activity score at Week 4
- Change from baseline in the SGRQ-C Impact score at Week 4

For details on the derivation of the above SGRQ-C scores refer to section 5.5.3

- Change from baseline in MRC breathlessness scales at Week 4

For details on the MRC scale refer to section 5.5.4

- Transition Dyspnea Index (TDI) at week 4
- Patient Global Assessment of Change (PGAC) at Week 4
- Change from baseline (average over the last 7 days of the run-in period) in average daily use of rescue medication over the treatment period, and at Week 1, 2, 3 and 4.
Average daily use of rescue medication is the average of the number of times the rescue medications is taken (multiplied by two as two puffs are taken at each administration) during the period of time.

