5.10 Rescue Medications

Short acting bronchodilators may be used as rescue medication. If this is inadequate for symptom control, the patient should contact the Investigator. Rescue medication use during each treatment visit must be separately documented in the eCRF (medication, dose, date and time of each administration). Protocol procedures must still continue even if rescue medication has been taken. Rescue medication (i.e. albuterol/salbutamol) use will be captured in the electronic diary (e-diary).

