Average EXACT-PRO total scores, average daily use of rescue medication, SGRQ-C total scores, MRC, global assessment of change, and TDI scores will be compared between the five treatments using ANCOVA models with treatment and country(/center) as factors and using baseline as a covariate where appropriate. Subdomain scores of the EXACT-PRO and SGRQC will be summarized and subjected to exploratory analyses.

The number of COPD exacerbations will be summarized by treatment group.

Testing for efficacy will start with the highest dose of RPL554 versus placebo. If a statistically significant difference is found, the testing will proceed with the next highest dose, and so on. Secondarily, the various doses of RPL554 will be compared. Appropriate measures will be taken to control for the type I error rate in these hypothesis tests. A closed testing procedure to test active dose vs. placebo will be used for the primary endpoint. The study is not powered for pairwise differences between active doses. Thus, dose-response is best investigated in a secondary analysis fitting an appropriate dose-response model to the data. The Statistical Analysis Plan will provide additional details of the multiplicity adjustment method(s) used.

All hypothesis testing will be done using two-sided alternative hypotheses. P-values less than 5% will be considered statistically significant.

9.2.2.6 *Safety*

Safety data, including safety laboratory tests, ECG parameters, Holter monitors, vital signs and physical examinations, will be summarized by treatment group and time point, when appropriate. For continuous variables, the change from baseline (both regarding pre-dose at Visit 2 and pre-dose at each treatment visit) to each post-dose time point will also be calculated and summarized. Data will further be illustrated by shift tables (showing changes from low/normal/high) and shift plots for selected time points.

Coded adverse event terms will be presented by system organ class (SOC) and preferred term and summarized by treatment group. A summary table by treatment group with total number and number of patients with adverse events, SAEs, adverse events leading to discontinuation of study medication, causally related adverse events and severe adverse events will be produced. Further SAEs, causally related adverse events and adverse event of each intensity will be summarized by SOC and preferred term.

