3.4. Changes in the Conduct of the Study or Planned Analyses

- The method for analysis the primary efficacy endpoint has been changed from LOCF ANCOVA to mixed model for repeated measures (MMRM). The change was led by the superiority of MMRM with respect to LOCF in avoiding some type of bias as suggested by Siddiqui et al. (Siddiqui O, 2009)
- Introduction of Per Protocol analysis set. This is an analysis set of interest for a phase II study.

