5.5. Efficacy Endpoints details

5.5.1. Pulmonary Function Tests

Baseline FEV₁ is defined as the FEV₁ pre-dose assessment (-15 minutes) collected at Visit 2.

Peak FEV₁ (over 3 (12) hours) is defined as the maximum post-dose value among the values collected up to 3 (12) hours.

Morning trough FEV₁ is defined as the last pre-dose value at the visit under analysis

Average FEV₁ (over 3 (12) hours) is defined as the Area under the curve AUC₀₋₃ (AUC₀₋₁₂) of the FEV₁ values collected during the visit under analysis, divided by the length of the time (in hours) interval of interest. The AUC is calculated using the trapezoidal rule.

Parameters will be calculated over 3 hours (at Day 1 and Week 1 to 4) and over 12 hours (Day 1 and Week 4).

If patient miss hour 2 and 3 then the AUC 0-3 is set to missing. If patient miss hour 8 and 12 then AUC 0-12 is set to missing.

Censoring of value after rescue medications: before derivation of endpoints, within each visit, the spirometry data collected after the use of rescue medications (either Albuterol / Salbutamol or Ipratropium as collected on the CRF) will be censored (i.e.: considered as missing)

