5.6.2. Analysis of Primary Endpoint

The primary efficacy analysis parameter is change from baseline FEV₁ to peak FEV₁ at Week 4 of treatment. The primary analysis will be based on the full analysis set.

Summary statistics for FEV₁ will be presented for baseline, week 4 and change from baseline by treatment group on patients with both assessments.

The primary analysis will use a restricted maximum likelihood (REML)–based repeated-measures approach. The change from baseline FEV₁ (at Day 1, Week 1, 2 3 and 4) will be the dependent variable. The analyses will include the fixed, categorical effects of treatment, visit, and treatment-by-visit interaction as well as the continuous, fixed covariates of baseline value. An unstructured (co)variance structure shared across treatment groups will be used to model the within-patient errors. If the model does not converge a compound symmetry (co)variance structure will be used. The Kenward-Roger approximation will be used to estimate denominator degrees of freedom and adjust standard errors. Analyses will be implemented with SAS PROC MIXED (see Appendix 4: SAS code for efficacy analysis). The primary comparison will be the contrast (difference in least squares mean [LSMEAN]) between treatments at Week 4.

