5.6.3. Analyses of Secondary and exploratory Endpoints

The secondary and exploratory endpoints will be analyzed in the same way as the primary endpoint.

In the analysis of TDI, BDI scores will be used as baseline in the model and the dependent endpoint will be the TDI score.

As for PGAC the model will not include the baseline as the score reflect itself a change from baseline.

The number of COPD exacerbations and use of rescue medications will be summarized by counts and percentages.

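### SAP 5.6.3 does not settle whether change in average daily rescue use is compared between groups or only tabulated, and the primary model does not fit the treatment-period average

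*SAP*

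**What the plan says.** The endpoint in SAP 5.2 is "Change from baseline (average over the last 7 days of the run-in period) in average daily use of rescue medication over the treatment period", plus the same change at Weeks 1, 2, 3 and 4. Each administration counts as two puffs, so the variable is a mean number of puffs per day.

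SAP 5.6.3 begins: "The secondary and exploratory endpoints will be analyzed in the same way as the primary endpoint". Two sentences then adapt that rule for individual endpoints. The Transition Dyspnea Index (TDI) uses the Baseline Dyspnea Index as its baseline, and the patient global assessment (PGAC) has no baseline term. The section ends: "The number of COPD exacerbations and use of rescue medications will be summarized by counts and percentages".

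The primary analysis in SAP 5.6.2 is a repeated-measures model: "The analyses will include the fixed, categorical effects of treatment, visit, and treatment-by-visit interaction", with the baseline value as covariate. SAP 5.6.5 treats the secondary endpoints as exploratory but has each of them tested nominally, stepping down through the doses.

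Protocol 9.2.2.5 calculates average daily rescue use for the full treatment period and for each week. It then plans an ANCOVA in which "average daily use of rescue medication, SGRQ-C total scores, MRC, global assessment of change, and TDI scores will be compared between the five treatments", with treatment and country (or center) as factors and baseline as covariate where appropriate. Both documents list comparison of the amount of rescue albuterol/salbutamol as a secondary objective (section 2.2 in each). SAP 3.4 lists two departures from the protocol: the MMRM for the primary endpoint and the new per-protocol set.

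**The concern.** Counts and percentages do not estimate a difference in mean puffs per day. SAP 5.2 also defines no yes/no variable for rescue use, and no period over which it would be counted, so the closing sentence of 5.6.3 points to a summary that the endpoint definition does not supply.

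A programmer who follows that sentence literally would produce a table and no treatment contrast. A named secondary objective would then go unanswered, and a comparison planned in the protocol would disappear without being recorded as a change. A programmer who follows the opening sentence would produce contrasts for Weeks 1 to 4, but would have to improvise for the average over the whole treatment period.

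**Working it through.** No figure in the plan concerns rescue use. The only sample-size statement (SAP 3.3, protocol 9.3) is for peak FEV₁. It reproduces: 250 × √(2/80) × (1.960 + 0.8416) = 110.7 mL, against the stated 111 mL. It has no bearing here, so the check is a comparison of the texts.

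1. **Type of variable.** SAP 5.2 defines a continuous change from a 7-day baseline. Its natural summary is a mean and its natural comparison a difference in means. Protocol 9.2.2.5 treats it that way.

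2. **Role of the closing sentence in SAP 5.6.3.** It covers two things at once: COPD exacerbations and rescue use. SAP 5.3 defines an exacerbation as a patient having a qualifying adverse event with steroid use. That outcome has no baseline value and no series of visit values, so a model for change from baseline cannot apply to it. For exacerbations, the sentence must therefore replace the opening rule. Nothing in it says that rescue use is treated differently. It also follows the TDI and PGAC sentences, which both modify the opening rule, so reading it as a further exception is natural.

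3. **Evidence against that reading.** The opening sentence covers all secondary endpoints, and rescue use is listed as one in SAP 5.2. SAP 5.6.5 has each secondary endpoint tested. The closing sentence speaks of summarizing and not of analysing. On this evidence, the counts are an addition.

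4. **The protocol and the change log.** The protocol compares the five groups by ANCOVA. SAP 3.4 records no move to description for rescue use. If such a move was intended, it is undocumented. If it was not, the closing sentence needs rewording.

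5. **Whether the opening rule is enough.** There are two forms of the endpoint:
   - *Weeks 1 to 4:* four values per patient, so treatment, visit and treatment-by-visit terms and an unstructured covariance can all be fitted. The primary model works, with baseline rescue use as the covariate.
   - *Treatment period:* one value per patient. Visit has a single level, so the visit and interaction terms drop out and there is no within-patient covariance to model. The code in SAP Appendix 4, which asks for treatment-by-visit means, cannot be applied as written. One analyst might reduce it to an ANCOVA on treatment and baseline, another might use the protocol's ANCOVA with country, and a third might average the weekly contrasts from the MMRM. The SAP does not choose among them.

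Step 5 leaves a gap under either reading of the closing sentence.

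**The case against.** The strongest reply is that the SAP, read as a whole, already requires the comparison. SAP 5.6.3 opens with a rule for all secondary endpoints, 5.6.5 says each is tested by dose, and a count table cannot deliver such a test, so the closing sentence must be an added description. This has force. A reader might infer that the SAP has abandoned the between-group comparison, and the documents do not support that. They contain two rules that point different ways and no statement of which prevails. The reply does not remove the problem, because the same sentence must act as a replacement for exacerbations, and because the treatment-period average has no workable model even on the favourable reading.

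Three further inferences are tempting and should not be drawn.

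- **That it is open whether ipratropium counts.** Protocol 5.10 does say "Short acting bronchodilators may be used as rescue medication", and SAP 5.5.1 includes ipratropium. The latter serves only to censor clinic spirometry from CRF data. The objectives in both documents, the endpoint in protocol 9.2.1.2 and the diary descriptions in protocol 5.10 and 7.2.2 all name albuterol/salbutamol. SAP 5.2 could repeat the drug name, but the meaning is recoverable.
- **That permitted scheduled albuterol makes the endpoint invalid.** The diary is described by drug, with no split between scheduled and as-needed doses. The resulting count is total albuterol/salbutamol use, which is a valid randomized comparison. This is a matter of labelling.
- **That power is lost by moving from means to percentages.** No test of percentages is planned, and the documents give no mean, spread or expected effect for rescue use. Any power figure would rest wholly on assumed inputs.

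**Conclusion.** The point stands as a conflict between rules in SAP 5.6.3, plus a missing model for one of the two forms of the endpoint. If the counts sentence governs, a named objective loses its between-group estimate, contrary to protocol 9.2.2.5 and without an entry in SAP 3.4. If the opening rule governs, Weeks 1 to 4 are covered and the treatment-period average is not.

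Severity is minor. SAP 5.6.5 makes secondary endpoints exploratory, rescue use is not among the selected endpoints in SAP 5.4, and neither the primary analysis nor its error control is affected. The conclusion depends only on the wording of the two documents. No numerical size is claimed.

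**What to change.** In SAP 5.6.3, remove rescue medication from the counts sentence, leaving COPD exacerbations there, and add wording such as:

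> Change from baseline in average daily albuterol/salbutamol use, as recorded in the e-diary, will be compared with placebo for each dose. Weeks 1 to 4 will be analysed with the primary MMRM, using baseline rescue use as covariate. The treatment-period average will be analysed by ANCOVA with treatment and country as factors and baseline rescue use as covariate, as in protocol 9.2.2.5. Counts and percentages of use will be shown for description only.

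Name albuterol/salbutamol in the SAP 5.2 endpoint as well, to match the objective.

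The cost is a few sentences and one extra ANCOVA that the protocol had already planned. Data collection, visits and the diary are unchanged. One limitation remains: daily puff counts are usually skewed, so the confidence intervals from these models will be approximate.

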5.3. Exploratory Efficacy Endpoints

- Change from baseline in EXACT-PRO E-RS score at Week 1, 2 and 3
- Change from baseline in EXACT-PRO Total score at Week 1, 2 and 3
- Change from baseline in EXACT-PRO E-RS Breathlessness score at Week 1,2 and 3
- Change from baseline in EXACT-PRO E-RS Cough/Sputum score at Week 1,2 and 3
- Change from baseline in EXACT-PRO E-RS Chest Symptoms score at Week 1,2 and 3

For details on the derivation of the above EXACT-PRO scores refer to section 5.5.2

- Change from baseline in the SGRQ-C Total score at Week 2
- Change from baseline in the SGRQ-C Symptoms score at Week 2
- Change from baseline in the SGRQ-C Activity score at Week 2
- Change from baseline in the SGRQ-C Impact score at Week 2

For details on the derivation of the above SGRQ-C scores refer to section 5.5.3

- Change from baseline in MRC breathlessness scales at Week 2

For details on the MRC scale refer to section 5.5.4

- Transition Dyspnea Index at week 2
- Patient Global Assessment of Change (PGAC) at Week 2
- COPD exacerbation
 - Patient with one adverse event with MedDRA Preferred Term='COPD exacerbation' and use of systemic steroids (ATC2=H02) from AE date of onset for at least three days
- Change in peak FEV₁ (over 12 hours) from Day 1 (single dose) to Week 4 (steady state)

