4.3.1 Study Medication Discontinuation

Study medication must be discontinued for the following reasons:

- Unacceptable toxicity related to study medication
- Intolerable or persistent adverse events of any severity
- General or specific changes in the patient's condition rendering the patient unacceptable for further treatment in the judgment of the Investigator
- Development of a COPD exacerbation, which necessitates use of oral or parenteral corticosteroids and/or antibiotics.
- Reduction from baseline (Visit 2) in pre-dose FEV₁ >20% that requires use of albuterol/salbutamol >12 puffs per day for at least 3 consecutive days associated with an increase in COPD symptoms.
- Pregnancy

Verona Pharma plc CONFIDENTIAL Page 28 of 67

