4.3.2 Patient Withdrawal

The patient has the right to withdraw at any time and for any reason, without explanation and without jeopardizing any subsequent treatment by the clinician, if applicable. However, anyone withdrawing should be encouraged to offer an explanation for their withdrawal particularly if it relates or is perceived to relate in any way to the study medication, or to the conduct of the study. Patients can also be withdrawn in case of protocol deviations and non-compliance. It should be made clear to patients that they are free to withdraw from the study at any time.

If a patient withdraws following randomization, every attempt should be made to contact the patient to determine the reason for withdrawal and to complete the recording of any available pharmacodynamic data and all adverse event data. If a patient agreed to enter the study and signed a consent form but withdrew from the study, or was withdrawn from the study, without receiving any study medication, no further follow-up is necessary.

All withdrawn patients should be contacted to have a final study visit. If it is considered by the Investigator that a patient requires greater medical supervision and/or investigations, an unscheduled visit prior to (and in addition to) the scheduled final study visit may be performed.

If a patient decides to withdraw voluntarily, or is withdrawn by the Investigator at any time, the reasons for withdrawal and results of all relevant tests will be recorded in the electronic case report form (eCRF).

Patients with an exacerbation of COPD, defined as increased symptoms for at least 3 days and decreased lung function requiring treatment with steroids or antibiotics, should be terminated from the study and given medical care to ensure their safety. Safety measures from the final study visit should be performed, if possible.

A female patient who becomes pregnant during the study must be withdrawn immediately. The Investigator will make all reasonable efforts to ascertain the progress and outcome of the pregnancy.

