7.6 Handling of Adverse Events and Pregnancies

7.6.1 Adverse Event Definitions

Adverse event is defined as any undesirable experience occurring to a patient, or worsening of patient's pre-existing condition, during a clinical study, whether or not considered related to the study medication. An adverse event may be any of the following:

- A new illness
- An exacerbation of a sign or symptom of the underlying condition under treatment or of a concomitant illness
- Unrelated to participation in the clinical study or an effect of the study medication
- A combination of one or more of the above factors

No causal relationship with the study medication is implied by the use of the term "adverse event."

An exacerbation of a pre-existing condition or illness is defined as a more frequent occurrence or as an increase in the severity of the pre-existing condition or illness during the

Verona Pharma plc CONFIDENTIAL Page 48 of 67

study. COPD exacerbations, for the purposes of this protocol, are defined as an increase or new onset of more than one respiratory symptom (cough, sputum, sputum purulence, wheezing, or dyspnea) lasting for at least 3 days and requiring treatment with an antibiotic, systemic steroid, or both (Decramer et al., 2009).

Planned or elective surgical or invasive procedures for pre-existing conditions that have not worsened are not adverse events. However, any complication that occurs during a planned or elective surgery is an adverse event (if the event fits the serious criteria, such as an extended hospitalization, it will be considered to be serious). Conditions leading to unplanned surgical procedures may be adverse events.

Adverse reaction is defined as all untoward and unintended responses to study medication related to any dose administered.

Serious adverse event (SAE) is any adverse experience that:

- Results in death
- Is life-threatening
- Requires inpatient hospitalization or prolongation of existing hospitalization
- Results in persistent or significant disability/incapacity, OR
- Is a congenital anomaly/birth defect
- Other medical events*

*Important medical events that may not be immediately life-threatening or result in death or hospitalization may be considered a SAE when, based on appropriate medical judgement, they may jeopardize the patient or may require medical or surgical intervention to prevent one of the outcomes listed above.

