This document describes the rules and conventions to be used in the presentation and analysis of efficacy and safety data for protocol RPL554-CO-203. It describes, in detail, the data to be summarized and analyzed, including specifics of the statistical analyses to be performed.

This statistical analysis plan is based on the final protocol version 2.0, dated 18th of April 2017.

2. Study objectives

The purpose of this study is to investigate the dose response of RPL554 in patients with Chronic Obstructive Pulmonary Disease (COPD) over 4 weeks. Clinical practice indicates that this length of time should allow for the study of the bronchodilator response (measured predominantly by peak FEV₁) and the anti-inflammatory response (measured predominantly by trough FEV₁).

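### SAP 5.3 counts a COPD exacerbation only with the coded adverse event plus at least three days of systemic steroid, whereas Protocol 7.6.1 also accepts antibiotics and applies the three days to symptoms

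*SAP*

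**What the plan says.** Protocol 7.6.1 gives a definition meant to serve the whole protocol: a worsening or new onset of more than one respiratory symptom, "lasting for at least 3 days and requiring treatment with an antibiotic, systemic steroid, or both". Two other protocol sections also accept antibiotics. Section 4.3.1 lists as a reason for stopping study medication "Development of a COPD exacerbation, which necessitates use of oral or parenteral corticosteroids and/or antibiotics". Section 4.3.2 describes an exacerbation that ends participation as "defined as increased symptoms for at least 3 days and decreased lung function requiring treatment with steroids or antibiotics". The planned analysis, in Protocol 9.2.2.5, is one sentence: "The number of COPD exacerbations will be summarized by treatment group".

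The SAP states its basis: "This statistical analysis plan is based on the final protocol version 2.0, dated 18th of April 2017". Among the exploratory endpoints, SAP 5.3 defines COPD exacerbation as a patient with one adverse event of that preferred term and "use of systemic steroids (ATC2=H02) from AE date of onset for at least three days". SAP 5.6.3 adds only this: "The number of COPD exacerbations and use of rescue medications will be summarized by counts and percentages". SAP 3.4, the section for changes to the planned analyses, has two entries: the move from LOCF ANCOVA to MMRM for the primary endpoint, and "Introduction of Per Protocol analysis set".

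**The concern.** The SAP's counting rule is not the protocol's definition. One of the two qualifying drug classes has gone, and the three-day condition now measures the length of steroid use instead of the length of symptoms. A patient treated with antibiotics alone could be taken off study medication under Protocol 4.3.1, and out of the study under 4.3.2, because of an exacerbation, yet not be counted in the exacerbation summary.

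At stake is the meaning of one descriptive table. A reader who sees counts of COPD exacerbations by dose would assume the protocol definition unless told otherwise.

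**Working it through.** The plan states no figure for exacerbations, so there is none to reproduce. The sample size rests on peak FEV₁ and does not depend on this endpoint. The check is a comparison of the texts.

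**Step 1. The rules side by side.**

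| Element | Protocol 7.6.1 | Protocol 4.3.2 | SAP 5.3 |
|---|---|---|---|
| Symptoms | more than one | increased, number not stated | no test; relies on the coded adverse event |
| What the three days measure | symptoms | symptoms | steroid use |
| Lung function | not mentioned | must be decreased | not mentioned |
| Qualifying drugs | antibiotic or systemic steroid | steroid or antibiotic | systemic steroid (H02) only |
| Minimum treatment length | none | none | three days, from adverse event onset |

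Protocol 4.3.1 gives no symptom test and accepts oral or parenteral corticosteroids or antibiotics. No protocol section supports a steroid-only rule.

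**Step 2. Apply 7.6.1 and SAP 5.3 to the same cases.** Each case is an adverse event coded as COPD exacerbation.

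| Case | Protocol 7.6.1 | SAP 5.3 |
|---|---|---|
| Symptom tests met, antibiotic only | counted | not counted |
| Symptom tests met, steroid under three days, with or without antibiotic | counted | not counted |
| Symptom tests met, steroid three days or more starting on the onset date | counted | counted |
| Symptom tests met, steroid three days or more starting after the onset date | counted | depends on how the onset phrase is read |
| One symptom, or symptoms under three days, with steroid three days or more from onset | not counted | counted |

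The first two rows are definite omissions. The last row shows that the SAP rule is not simply a subset of the protocol definition.

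**Step 3. Size.** The documents give no exacerbation rate, no share treated with antibiotics alone and no steroid-course lengths, so the effect cannot be computed. For scale, with the 80 patients planned per group (Protocol 9.3, SAP 3.3), one patient classified differently moves that group's percentage by 100 × 1/80 = 1.25 points, in either direction.

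As an illustration under assumed values only, let *a* be the share of protocol-defined events treated with antibiotics alone, and *s* the share of the remainder that meets the SAP's steroid condition. The share of protocol-defined events captured is (1 − *a*) × *s*.

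| *a* | *s* = 1.0 | *s* = 0.8 |
|---|---|---|
| 0.10 | 90% | 72% |
| 0.30 | 70% | 56% |
| 0.50 | 50% | 40% |

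These values are not estimates for this trial. They also leave out events that the SAP adds through the last row of Step 2.

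**Step 4. Counting unit.** SAP 5.3 is written per patient. Protocol 9.2.2.5 and SAP 5.6.3 speak of the number of exacerbations. The SAP does not say which the table will show.

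**The case against.** The strongest reply is that little depends on this. The endpoint is exploratory, is summarized only by counts and percentages, and is absent from the protocol's objectives and from its primary and secondary endpoints. SAP 6.1 and 6.1.1 tabulate treatment-emergent events by preferred term whatever the treatment, including those leading to study discontinuation. All of this stands and sets the severity. It does not restore the protocol-defined count, because those tables do not classify events by antibiotic or steroid treatment.

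A second reply is that a SAP may operationalise a definition, and that investigators may already have applied Protocol 7.6.1 when reporting the event. That may be so for the symptom tests. The added steroid filter would still remove antibiotic-only events and short courses.

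A third reply concerns disclosure. Protocol 9.1 requires deviations from the specified analysis to be detailed and justified in the clinical study report. A reader might infer from the silence of SAP 3.4 that the change would go unreported; the documents do not support that. What remains is that SAP 3.4 is the section for such changes and this one is not there.

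Two further inferences should be resisted. One is that the SAP count must always be the lower one; the last row of Step 2 shows why that does not follow. The other is to count the treatment patterns left out and quote the fraction as a magnitude. Such a fraction depends on how the patterns are divided and says nothing about how often they occur.

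**Conclusion.** The mismatch is confirmed, at minor severity. Followed as written, SAP 5.3 produces an exacerbation summary that omits antibiotic-only events and steroid courses under three days, contrary to the protocol's own definition, and SAP 3.4 does not list the change. Neither the size nor the net direction of the effect can be derived from the documents.

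This rests on reading SAP 5.3 literally, with the coded adverse event and the steroid condition both required, and on SAP 5.6.3 using that same rule, since it gives no other. The primary endpoint, its type I error control and the sample size are untouched. Omitted treatment-emergent events are not lost from the report; they are missing from one summary.

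**What to change.** The change concerns counting only and takes no view on the rules for stopping medication or leaving the study.

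*Preferred: align SAP 5.3 with Protocol 7.6.1.*
- Count adverse events coded as COPD exacerbation that were treated with a systemic steroid, an antibiotic, or the two together, where the drug's recorded indication is that event. Set no minimum treatment length.
- Apply the three days to event duration, stated to be a proxy for symptom duration. State that the more-than-one-symptom test rests on the investigator's adverse event report.
- Say how missing or partial adverse event stop dates are handled, since SAP 3.8.4 covers start dates only. Borrowing the medication convention of SAP 3.8.5 (end of month or year) could lengthen events past three days and raise the count.
- Report both the number of patients with an event and the number of events, and show the steroid-treated subset as a separate row.

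*Alternative: keep the narrower rule.* Label it *steroid-treated exacerbations*, say whether the steroid must start on the onset date or may start later, state the counting unit, and list and justify the change in SAP 3.4.

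*In either case,* reconcile Protocol 7.6.1 and 4.3.2 on number of symptoms and lung function, or name the one used for counting.

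*Cost.* The preferred route needs a short rewrite of SAP 5.3, an antibiotic code list, a stop-date rule and a small programming change. Event start and stop times (Protocol 7.6.2), COPD therapy dates (5.9.1) and all concomitant medications (5.9.2) are already collected. SAP 4.4 shows that medications are coded and that the log carries an indication; whether it links a drug to a specific event is not stated and should be checked. The alternative costs one label, one clarified phrase with its counting unit, and one entry in SAP 3.4.
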